7.4 Interim Analyses and Data Monitoring

7.4.1 Interim Analyses

The planned interim analyses will not be performed due the early termination of the study.

7.4.2 Data Monitoring

An Independent Data Monitoring Committee (IDMC) will be established to oversee the safety and efficacy of the study, will follow the FDA's Guidance on IDMCs/DSMBs and comply with ISO 14155. The IDMC will meet to assess safety after every 100 patients randomized or every 6 months, whichever occurs first, until the end of the study. Due to early termination of the study, only two safety DMC meetings took place. No interim analysis will be performed.

Further details regarding the IDMC can be found in the IDMC charter.

7.5 Multi-center Studies and Pooling of Centers

This is a multi-center study; the data from all sites will be pooled according to treatment group.

7.6 Multiple Comparisons/Multiplicity

No adjustments for multiple comparisons or multiplicity will be made.

7.7 Examination of Subgroups

No subgroup analyses will be performed due to the limited number of patients in this early terminated study.

8 STATISTICAL ANALYSIS

8.1 Disposition of Patients

The number of patients enrolled by region (North America, Europe and Asia), country and site will be presented.

The number of patients screened, the number of patients randomized, and the number of patients treated with the treatment to which they were randomized (ie, sorafenib or TheraSphere) will be summarized.

The number of patients who completed or were ongoing at the end of the study will be summarised. Note: patients who died will be considered as having completed the study.

The number of patients who discontinued from the study will be summarized overall and separately for those who were treated with TheraSphere or sorafenib. The reasons for discontinuation will be summarized for patients by treatment group.

This information will be summarized also by the stratification factor AFP \leq 400 ng/mL or >400 ng/mL).

8.2 Protocol Deviations/ Violations

Protocol deviations/violations will not be programmatically identified or entered into the database. However, protocol deviations/violations will be identified and categorized within an excel spreadsheet tracker managed by Chiltern's Clinical Department. Deviations will be categorized by BTG as major or minor. All protocol deviations/violations determinations will be finalized before database lock.

The number and percentage of patients within each category of deviation, separately for major and minor deviations, will be summarized for each treatment group and overall.

8.3 Analysis Populations

8.3.1 Treated Population

All randomized patients who received study treatment at least once will form the Treated Population and will be analyzed according to the treatment group to which they were randomized.

8.3.2 Safety Population

The Treated Population will be the same as the Safety Population, but will be analyzed according to the treatment actually received. This population will be used in all safety reporting and analysis.

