#### 9.2.16.1.2 THERASPHERE PRE-TREATMENT EVALUATION

Patients randomized to the Treatment arm must undergo the following evaluations to determine eligibility to receive the TheraSphere. These include:

- Hepatic Angiography: selective celiac and superior mesenteric arteriograms are needed to evaluate the hepatic arterial anatomy for the whole liver, as well as evaluation of potential sources of extrahepatic blood supply to tumors. The goal is to identify, within the hepatic vascular anatomy, a catheter placement location that allows a single TS infusion throughout the lobar tumor volume without administration of microspheres to extra-hepatic structures.
- A technetium-99m macroaggregated albumin (99mTc-MAA) scan is used to assess the potential for shunting microspheres to the lungs as well as the potential for the deposition of microspheres to the gastrointestinal (GI) tract. Repeat 99mTc-MAA may be needed for subsequent treatments to estimate cumulative lung shunt or re-asses GI flow. Note that 3 technical factors (time between administration of 99mTc-MAA and the scan, 99mTc-MAA particle size and the presence of free 99mTc-MAA) can lead to an over-estimation of shunting to the lungs.

TheraSphere should not be administered to a patient randomized to the Treatment arm if:

- Deposition of microspheres to the GI tract that cannot be corrected by placement of the catheter distal to collateral vessels or the application of standard angiographic techniques, such as coil embolization to prevent deposition of microspheres in the GI tract.
- Exposure of radiation to the lungs of 30 Gray (Gy) for a single infusion or a cumulative 50 Gy limit for all infusions of TheraSphere that cannot be corrected by dose reduction of TheraSphere.

In the event that a patient randomized to the TheraSphere arm is determined not to be suitable for and/or cannot be safely treated with TheraSphere, that patient will not receive TheraSphere and may proceed to treatment with SOC sorafenib regimen as described in Section 9.2.16.2.

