#### 10.2.1 Populations and Sub-Arms

- Intent to Treat population
- All randomized patients will be analyzed according to the treatment group to which they are assigned.
- Per Protocol Population (PPP)

All randomized patients will be analyzed according to the treatment actually received and adherence to the protocol. Patients who are determined to have major protocol violations as defined in Section 14 will be excluded from the PPP analysis

Safety Analysis Population (SAP)

All randomized patients who received study treatments at least once will be analyzed according to the treatment actually received.

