6.5.1.3 Extent of Study Exposure and Follow-up

The duration of survival follow-up and duration of follow-up from last study treatment will be determined.

Duration of survival follow-up (months) = (date of death/last known aliverandomization date + 1) / 30.4375

Duration of follow-up from last study treatment is defined as the time from last study treatment (TheraSphere or sorafenib) until date of death due to any cause or last contact date when patient was known to be alive.

Duration of follow-up (from last study treatment) (months) = (date of death/last known alive – date of last dose of study treatment + 1) / 30.4375

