6.5.2 Adverse Events

Treatment Emergent Adverse Events (TEAEs) are AEs which were not present at the initiation of sorafenib or first angiogram or worsened in severity following treatment. If the imputed AE start date starts on or after the first dose of sorafenib or first angiogram and prior to 30 days after last dose of sorafenib or TheraSphere then it is considered a TEAE unless the AE was an ongoing event (end date of one AE matches start date of the next) that started prior to first dose of sorafenib or first angiogram and the grade did not worsen.

The investigator's verbatim term of the AEs will be mapped to system organ classes (SOC) and preferred terms using the MedDRA Version 14.0 dictionary (Medical Dictionary for Regulatory Activities). The investigator will use the NCI Common Toxicity Criteria for Adverse Events [CTCAE] (version 4.0) or the protocol specific criteria when no NCI CTC criteria are available for the adverse event to determine the severity of the AEs.

Adverse events related to sorafenib, device, and angiographic procedures are defined as those events recorded on the eCRF with relationship of possibly, probably, or definitely related.

The incidence of TEAEs will be the number of patients who had the AE (counted only once per patient) divided by the number of patients in the safety population and represented as a percentage. The incidence of AEs will be the number of times an event with the same preferred term occurs, counting worsening events only once. For worsening events, the AE end date of the earlier AE will be the same as the start date of the same AE with a higher severity.

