8.10.2 Adverse Events

The investigator's verbatim term of each adverse event will be mapped to system organ class (SOC) and preferred term (PT) using the MedDRA dictionary version 14.0.

An overall summary of adverse events will be presented including number and percentage of patients with any TEAEs, sorafenib related TEAE, adverse device effects

(ADEs), angiographic procedure-related TEAEs, TEAEs CTCAE grade ≥ 3, serious adverse events (SAEs), serious adverse device events (SADEs), TEAEs with outcome of death and TEAEs leading to discontinuation of sorafenib.

TEAEs will be summarized by SOC and PT; a patient will only be counted once per system organ class and once per PT within a treatment. Patient counts and percentages and event counts will be presented for each treatment group:

- Overall summary of AEs
- All TEAEs.
- All TEAEs of CTCAE grade ≥3.
- All TEAEs related to sorafenib.
- All TEAEs related to device (ADE).
- All CTCAE grade ≥3 TEAEs related to device.
- All TEAEs related to angiographic procedure.
- All TEAEs with outcome of death.
- All treatment emergent serious adverse events (SAEs).
- All treatment emergent serious adverse device events (SADEs)
- All TEAEs leading to sorafenib discontinuation.

For the summary of AEs by CTCAE grade, if a patient has multiple events occurring in the same SOC or same PT, then the event with the highest CTCAE grade will be counted. For AEs by relationship to study device, if a patient has multiple events occurring in the same SOC or same PT, the event with the highest association to study device will be summarized (unknown relationship to study device will be considered related to study device).

All TEAEs and TEAEs grade ≥3 will be summarized by preferred term with descending frequency. In addition TEAEs will be presented by CTCAE grade (1-2, 3-4 and 5).

No statistical inference between the treatments will be performed on AEs.

Listings will be presented by patient for all AEs as well as for SAEs including SADEs, AEs with outcome of death, and AEs leading to discontinuation of sorafenib.

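### The Safety Population requires TheraSphere or sorafenib, but the treatment-arm safety clock starts at the first angiogram, so never-infused patients are missing from the safety tables or shown under sorafenib

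*SAP*

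**What the plan says.** **Who enters the safety set.** SAP 8.3.1: "All randomized patients who received study treatment at least once will form the Treated Population". SAP 8.3.2 carries those patients over and groups them as treated: "The Treated Population will be the same as the Safety Population, but will be analyzed according to the treatment actually received". It adds: "This population will be used in all safety reporting and analysis". Protocol 10.2.1 has the same rule: "All randomized patients who received study treatments at least once will be analyzed according to the treatment actually received".

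**What study treatment means.** There is no formal definition. SAP 6.5.1.3 measures follow-up as "the time from last study treatment (TheraSphere or sorafenib) until date of death due to any cause", and SAP 8.1 names the same two treatments when it counts treated patients. Neither names the angiogram.

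**When harm starts to count.** SAP 6.2.1 sets safety day 1 at the first sorafenib dose in the control arm and at the first angiogram in the treatment arm. SAP 6.5.2 defines TEAEs as "AEs which were not present at the initiation of sorafenib or first angiogram", or those that worsened after treatment. The window closes 30 days after the last sorafenib or TheraSphere dose. SAP 8.10.2 plans a separate table: "All TEAEs related to angiographic procedure".

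**What happens after a failed work-up.** Protocol 9.2.15 places randomisation ahead of the angiogram. Under Protocol 9.2.16.1.2, if TheraSphere proves unsuitable or unsafe, "that patient will not receive TheraSphere and may proceed to treatment with SOC sorafenib regimen". The synopsis and Protocol 9.1.3.1 also allow for this.

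**The concern.** The event clock and the entry rule start at different points. The clock opens at the angiogram, which treats the work-up as part of the TheraSphere strategy. Entry waits for an infusion or a sorafenib dose. Between the two are patients who had angiography, an MAA scan and possibly embolisation, but no infusion.

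Their work-up events belong to the TheraSphere pathway by the protocol's own account. Protocol 12.3.1 lists screening, procedure, embolisation and radiation as ways an event can relate to TheraSphere, and says this attribution is not appropriate for the control arm. Yet the as-treated rule gives these patients no place in the TheraSphere column. At stake are the completeness of the angiographic-procedure table and the meaning of the between-arm safety display. The primary endpoint is not affected by this point.

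**Working it through.** The plan states no figure that depends on this rule, so there is nothing to reproduce. The check is a cross-reading followed by an illustration.

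**Step 1: follow each kind of treatment-arm patient through the rules.**

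| Path after randomisation | In Safety Population? | Column | Work-up events |
|---|---|---|---|
| Angiogram, then TheraSphere | Yes | TheraSphere | Counted from the angiogram |
| Angiogram, then neither treatment | No | None | In no summary table |
| Angiogram, then sorafenib only | Yes | Sorafenib | Depends on which clock applies |

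For the third row the two clock rules differ. SAP 6.2.1 goes by arm, so the clock starts at the angiogram and work-up events enter the sorafenib column's all-cause and grade ≥3 counts. SAP 6.5.2 gives sorafenib start or first angiogram as alternatives without saying which governs a patient who has both. If sorafenib start is used, earlier work-up events are not treatment-emergent unless they worsen.

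For the second row the TEAE window has no end, because there is no last dose of either treatment. No section of either document provides a work-up-only group or column.

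**Step 2: illustrate the size.**

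Input from the documents: 320 patients planned at 1:1 (Protocol 10.1 and 9.2.15), so 320 / 2 = 160 per arm.

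Assumptions, none of them in the documents:
- every treatment-arm patient has an angiogram;
- the share never infused, f, is 5%, 10% or 20%;
- the risk of a work-up event is a = 10% in infused patients and b = 10% or 30% in never-infused patients.

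Formulas:
- never infused = 160f
- events in the TheraSphere column = 160(1 − f)a
- events in all patients with an angiogram = 160(1 − f)a + 160fb
- rate in the TheraSphere column = a; rate in all with an angiogram = (1 − f)a + fb

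| f | Never infused | Events, TheraSphere column | Events, all with angiogram (b = 10%) | Rate | Events, all with angiogram (b = 30%) | Rate |
|---|---|---|---|---|---|---|
| 5% | 8 | 152 × 0.10 = 15.2 | 15.2 + 0.8 = 16.0 | 10.0% | 15.2 + 2.4 = 17.6 | 11.0% |
| 10% | 16 | 144 × 0.10 = 14.4 | 14.4 + 1.6 = 16.0 | 10.0% | 14.4 + 4.8 = 19.2 | 12.0% |
| 20% | 32 | 128 × 0.10 = 12.8 | 12.8 + 3.2 = 16.0 | 10.0% | 12.8 + 9.6 = 22.4 | 14.0% |

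The TheraSphere column shows 10.0% in every row. The count falls in every row, but the percentage is too low only when b exceeds a.

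**Step 3: the sorafenib column.** Assume also that all never-infused patients take sorafenib, that 160 control patients are treated, and that the angiogram clock applies. Work-up events then contribute 160fb / (160 + 160f). The low end is 0.8 / 168 = 0.5% (f = 5%, b = 10%). The high end is 9.6 / 192 = 5.0% (f = 20%, b = 30%). If none of them take sorafenib, their events appear in no Safety Population table.

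**The case against.** **The angiogram might count as study treatment.** Protocol 9.2.16, headed as study treatments, contains the pre-treatment evaluation, and safety day 1 is the angiogram. A programmer could read it that way. SAP 6.5.1.3 and 8.1 name only TheraSphere and sorafenib, however, and Protocol 9.2.16.1.2 treats the work-up as deciding whether TheraSphere can be given. The narrower reading is the likelier one, but it is an inference. What stands is that the SAP needs to say which is meant.

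**A reader might infer that these events disappear.** The documents do not support that. Protocol 12.3 records adverse events from consent to study exit for randomised patients. SAP 7.1 plans listings of all case report form data, and SAP 8.10.2 plans listings by patient. The loss is from the summary tables. Listings give no incidence or denominator.

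**A reader might infer that work-up harm becomes sorafenib toxicity.** It does not. SAP 6.5.2 and 8.10.2 separate events related to sorafenib, to the device and to the angiographic procedure. An event coded as procedure-related would show as such, even in the sorafenib column. The misplacement affects the all-cause and grade ≥3 tables.

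**A reader might infer that TheraSphere is made to look safer.** As a rate, that requires more work-up harm in never-infused patients. The documents give no evidence either way.

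**The rule is prespecified and no AE testing is planned.** Both are true: Protocol 10.2.1 has the same set, and SAP 8.10.2 rules out inference on adverse events. The descriptive tables are still incomplete.

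**Conclusion.** The mismatch holds on the text, given that study treatment means TheraSphere or sorafenib. Work-up-only patients are left out of all Safety Population summaries. Patients who switch to sorafenib are tabulated under it, and their work-up events either enter that column's all-cause and grade ≥3 counts or are not treatment-emergent, depending on the clock. The event count for the TheraSphere pathway is understated whenever such patients have work-up events.

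The size is unknown. Under the assumed 5% to 20%, 8 to 32 of 160 planned patients would be affected. SAP section 5 reports early termination, so real numbers are probably smaller. The SAP should be changed because the gap alters safety attribution and the remedy is cheap.

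**What to change.** 1. Define the Safety Population as all randomised patients with a first angiogram (treatment arm) or a first sorafenib dose. Align Protocol 10.2.1, or record the departure in SAP section 5.
2. Use all patients with an angiogram as the denominator for the angiographic-procedure table.
3. Show work-up-only patients, and those who switch to sorafenib, in a separate column. Attribute events before the first sorafenib dose to the work-up.
4. State the TEAE start and end for these patients. One option is from the first angiogram to 30 days after the last work-up procedure, or to the first sorafenib dose if earlier. This keeps the 30-day length already in SAP 6.5.2.

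The data are already collected. The cost is revised wording, one extra column, and a TheraSphere safety group that is slightly more mixed.

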8.4 Demographic and Other Baseline Characteristics

Demographic and baseline summaries will be presented for the Treated Population and Safety Population.

Gender, race, and ethnicity, age category (≥18-<65 years, ≥65 years), AFP (≤400 ng/mL or >400 ng/mL), and ECOG performance score will be summarized using counts and percentages. Continuous variables such as age, AFP, time from diagnosis of HCC to randomization will be summarized with descriptive statistics (number of patients [n], mean, standard deviation [sd], median, minimum [min], and maximum [max]). Ethnicity responses of "Not Applicable" will be summarized under "Not Reported or Not Known".

Details of categorization of PVT at screening (venous location of PVT, tumor location, categorization of PVT) will be summarized using count and percentages.

History of hepatocellular carcinoma (HCC) will be summarized as the number and percent of patients who have portal hypertension, presence of cirrhosis, whether HCC is the first oncology diagnosis, and etiology.

Weight will be displayed in kilograms (kg), height will be displayed in centimeters (cm), and temperature will be displayed in Celsius (C). BMI (kg/m²) will be calculated as weight (kg) divided by height (m) squared. Weights, heights, or temperatures recorded in alternate units will be converted to the units being displayed using standard conversion formulas.

8.5 Physical Examination

Physical examinations are collected at screening only. The number and percent of patients with abnormal physical examination findings at screening will be summarized overall and by body system.

8.6 Baseline Tumor Burden and Liver Volume

Liver volume (mL), liver mass (kg), and tumor replacement (%) (percent of total liver volume occupied by tumor(s)) will be summarized using descriptive statistics (n, mean, sd, median, min, and max).

Liver mass will be calculated as:

Liver mass (kg) = liver volume (mL)*0.00103.

Total tumor replacement > 70% and >50% will be summarized using frequency counts and percentages. For patients whose total tumor replacement is >50%, number and percentage of those patients with albumin <3 mg/dL will be summarized.

8.7 Medical History

The number and percent of patients with medical history events will be summarized by system organ class and preferred term.

8.8 Prior and Concomitant Therapy

The World Health Organization Drug Dictionary (WHO DD) March 2011 will be used to classify medications by preferred term and WHO Anatomical Therapeutic Chemical (ATC) classification of ingredients.

The following applies to all data collected on the prior and concomitant eCRF page, medical history HCC eCRF page, and the best available care post progression eCRF pages and will be reported by each category separately.

Where a medication start date is missing, this medication will be assumed to be concomitant for reporting purposes, unless the end date is prior to the first dose of sorafenib or angiogram. Partial dates will be imputed as discussed in section 7.3.1.

Descriptive statistics, such as frequency counts and percentages will be provided to summarize the use of medications other than the study drug reported throughout the study. The number and percent of patients who took other therapy will be shown by WHO ATC classification of ingredients and by preferred term.

8.8.1 Prior Medication

A prior medication is defined as any medication given prior to first dose of sorafenib or date of angiogram.

The number and percentage of patients who had at least one prior medication will be tabulated as well as the number and percentage of patients with each medication. Patients will only be counted once for each medication.

8.8.2 Prior Oncologic Therapy for HCC

Prior HCC treatment type: Liver Directed Therapy, Prior Resection, and Systemic Treatment will be summarized from the Medical History of HCC eCRF page. Type of therapy/resection/treatment will be listed.

8.8.3 Concomitant Medication

A concomitant medication is defined as any medication given prior to and continuing after the first dose of sorafenib or date of angiogram, or any medication that is initiated on or after first dose of sorafenib or date of angiogram. Medications are considered concomitant through to the end of the study.

The number and percentage of patients who had at least one concomitant medication will be tabulated as well as the number and percentage of patients with each medication. Patients will only be counted once for each medication.

8.8.4 Best Available Care Post Progression

For best available care post progression, the number and percentage of patients receiving each medication will summarized by ATC class and medication.

Best available care procedure will be summarized as the number and percentage of patients by procedures: Resection, Ablation, and Other.

8.9 Analysis of Efficacy Parameters

Efficacy endpoints will be analysed using the Treated Population.

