# Treatment Arm Study Treatment (TheraSphere)

Within 2 weeks from randomization, hepatic angiography will be performed to assess hepatic vascular anatomy and tumor hypervascularity, followed by a 99mTc-MAA scan to rule-out gastrointestinal flow or unacceptable lung shunting. Embolization may be performed, if necessary, to close off gastrointestinal flow or to perform tumor redistribution so that the patient can meet eligibility criteria.

Patients will not be eligible for TheraSphere infusion if the potential radiation dose to the lungs exceeds 30 Gy for a single treatment or cumulative 50 Gy or embolization cannot be performed to effectively block GI blood flow from the hepatic arterial system. If radiation exposure to the lungs exceeds 30 Gy, dose reduction of TheraSphere is permitted (minimum dose allowed is 80 Gy ± 10%). These patients will be eligible to receive sorafenib SOC therapy and will be included in the Treatment Arm Intent-to-Treat analysis, but not in the Treatment Arm Per-Protocol analysis.

TheraSphere Treatment: TheraSphere treatment should occur within 28 days of randomization. The number of infusions required to achieve lobar treatment will be determined by the Investigator, based on the hepatic vascular anatomy.

Patients will receive TheraSphere, at a dose consistent with the approved product label, to the treated lobe of the liver. A target dose of 120 Gy ± 10% is advised. Thera Sphere Re-treatment: Re-treatment of the same patient/lobe with further cycles of TheraSphere is permitted if a treatable progression is detected during follow-up evaluations. Any retreatment should take place at least 28 days from the last TheraSphere treatment administered to that lobe. Patients can receive a subsequent TheraSphere administration in the absence of radiological progression criteria at investigator discretion. Patients must meet initial eligibility criteria to receive subsequent treatments. A maximum of three (3) TheraSphere administrations are permitted in total.

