#### 10.2.3 EFFICACY ANALYSIS

The efficacy analyses will be performed on the ITT and PPP populations.

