#### 10.2.3.2 SECONDARY ENDPOINT STATISTICAL ANALYSIS PLAN

For secondary efficacy endpoints, each comparison between treatment groups will be conducted at the final analysis with α=0.05 (two-sided). Secondary study endpoints will be analyzed only at the final analysis to determine the statistical significance, if any between, the Treatment and Control groups.

- Time to progression (TTP) will be calculated as the interval between the randomization date and the date of first disease progression as defined by the respective criteria noted below, death for any cause or of last contact for patients alive. The Kaplan-Meier method will be used to estimate the TTP curves in the two treatment arms; comparison between the curves will be performed using the log-rank test. Median TTP will be reported. Progression will be assessed separately using:
  - RECIST v1.1 criteria
  - mRECIST criteria
  - EASL response criteria (assessed bidimensionally on enhancing tissue)
- Time to symptomatic progression (TTSP) will be calculated as the interval between the randomization date and symptomatic progression, defined as assessment of ECOG performance status ≥2 with or without tumor progression based on imaging. Deterioration in performance status is to be observed at one subsequent evaluation 8 weeks later. For subjects who had not progressed symptomatically at the time of analysis, TTSP will be censored at their last date of PS assessment. The Kaplan-Meier method will be used to estimate the TTSP curves in the two treatment arms; comparison between the curves will be performed using the log-rank test. Median TTSP will be reported.
- Tumor response rate. The response probability will be estimated in each of the two treatment arms as proportion of CR+PR over the total number of ITT or PPP patients. The disease control rate (ie, CR+PR+SD) will also be compared between the treatment arms. The minimum time between image acquisitions is 6-8 weeks. Tumor response rate will be assessed separately using:
  - RECIST v 1.1
  - mRFCIST
  - EASL

Tumor response will be compared using the continuity adjusted Newcombe-Wilson test, and the 95% confidence limits will be calculated

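### The SAP analyses overall survival and every other efficacy endpoint only in treated patients; the protocol requires ITT and per-protocol sets, and the SAP's list of changes omits the switch

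*SAP*

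**What the plan says.** **Protocol.** Section 10.2.1 defines the ITT population: "All randomized patients will be analyzed according to the treatment group to which they are assigned". Section 10.2.3 then says: "The efficacy analyses will be performed on the ITT and PPP populations". For response, Section 10.2.3.2 sets the rate as the "proportion of CR+PR over the total number of ITT or PPP patients". The synopsis (Treatment Arm Study Treatment) says that patients found ineligible for infusion at work-up "will be included in the Treatment Arm Intent-to-Treat analysis, but not in the Treatment Arm Per-Protocol analysis". Section 9.2.15 keeps patients of either arm who cannot have their planned treatment under follow-up in that arm for ITT.

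**SAP.** Section 8.9 says: "Efficacy endpoints will be analysed using the Treated Population". Section 8.3.1 defines the set: "All randomized patients who received study treatment at least once will form the Treated Population", analysed as randomised. Section 8.3.2 adds: "The Treated Population will be the same as the Safety Population, but will be analyzed according to the treatment actually received". No ITT or per-protocol set is defined, and nothing in 8.9.1 or 8.9.2 overrides 8.9. Section 5, on changes, lists two items: the dropped interim analyses and the removal of death from time to progression (TTP). Section 4.2 still gives intent-to-treat analysis as the reason for following untreated patients.

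**The concern.** Randomisation comes before the angiogram (Protocol 9.2.15), so whether a patient can be treated is settled afterwards, and differently in each arm. Control patients start sorafenib within 2 weeks (Protocol 9.2.16.2). TheraSphere patients must first pass angiography and a 99mTc-MAA scan, and the synopsis says: "TheraSphere treatment should occur within 28 days of randomization". The trial is open-label, and OS still runs from randomisation (SAP 6.4.1).

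Limiting the analysis to treated patients removes deaths before treatment and patients who never start, possibly in unequal numbers. The primary comparison then loses part of the protection that randomisation gives, and a reader of SAP Section 5 would not know it.

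For response, SAP 6.4.2.4 counts patients with no post-baseline assessment as non-responders. That rule cannot help untreated patients, who have already left the denominator.

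**Working it through.** **1. The plan's own design figure.** Inputs from SAP 4.4 and Protocol 10.2.3.1: HR 0.69 (medians 9 and 13 months), analyses at 125, 188 and 250 deaths, two-sided alpha 0.05, rho = 1.5. With drift √(D/4)·|ln HR| and exact group sequential integration, power at 250 deaths is 80.7% (HR 0.69) or 79.9% (HR 9/13), so the stated 80% reproduces. Expected deaths with 320 patients, 42 + 12 months and 5% loss: 160 × (0.882 + 0.790) × 0.95 ≈ 254. Restoring ITT changes none of these design figures.

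**2. Populations side by side.**

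| Item | Protocol | SAP |
|---|---|---|
| OS and secondary efficacy | ITT and per-protocol | Treated only |
| Response denominator | ITT or per-protocol | Specified population, hence Treated |
| Never treated | Kept in assigned arm for ITT | Excluded (though 4.2 cites ITT) |
| Listed in SAP Section 5 | – | No |
| Safety | Received treatment, as treated | Same |

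Adverse-event analyses are therefore unaffected.

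**3. Illustration (a): only deaths before treatment are dropped; true HR 1.00.** Assumed: exponential survival with median 9 months in both arms; sorafenib start uniform on days 0–14, TheraSphere on days 14–28. Daily hazard λ = ln 2/(9 × 30.4375) = 0.00253. For a start uniform on days a to b:

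fraction removed = 1 − (e^(−λa) − e^(−λb))/(λ(b − a))

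This gives 1.75% of control and 5.17% of TheraSphere patients. Simulated Cox HRs (1,000,000 per arm, Monte Carlo SE at most 0.002):

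| First-28-day hazard | HR | HR, censored at 12–54 months |
|---|---|---|
| Full design hazard | 0.965 | 0.961 |
| Half | 0.983 | 0.981 |
| Quarter | 0.991 | 0.990 |

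Full hazard is pessimistic, since eligibility requires life expectancy above 3 months, Child-Pugh A and ECOG 0–1. The start window matters too: at full hazard, days 7–28 gives 0.975 and days 0–28 gives 0.985.

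**4. Illustration (b): all TheraSphere work-up failures are dropped, with no early-death filter; the same frail mix is in both arms.** If 5% fail with 1.5 times the hazard, HR = 0.983; if 10% fail with twice the hazard, 0.951. Dropping the same patients from control instead gives 1/0.983 = 1.02 and 1/0.951 = 1.05. Both effects together, at half early hazard, give 0.966 and 0.932.

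A harsher variant drops 5%, 10% or 15% of the TheraSphere arm, with median OS 3–5 months in those patients against 9 in the rest. It gives HRs of about 0.96–0.99, 0.93–0.95 and 0.88–0.93. With 320 randomised, two-sided type I error at nominal 0.05 becomes about 5–6%, 7–9% and 9–17%.

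**5. Sampling error for comparison.** The 95% CI around HR 1.00 is exp(±1.96 × 2/√d): 0.78–1.28 at the planned 250 deaths; 0.68–1.48 and 0.57–1.74 at an assumed 100 and 50 deaths after early termination.

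**6. Response rate.** If a fraction u of an arm is untreated and would count as non-responders, dropping them multiplies that arm's rate by 1/(1 − u): 1.05 at 5%, 1.11 at 10%. The between-arm ratio changes by (1 − u_control)/(1 − u_TheraSphere): 0.95/0.90 = 1.06 for 5% control against 10% TheraSphere, 0.90/0.95 = 0.95 for the reverse, and 1.00 if equal. The rate difference reported under SAP 8.9.2.4 scales by 1/(1 − u) even when u is equal.

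**The case against.** The Treated Population is analysed as randomised, so this is a modified ITT set and only never-treated patients leave it. SAP 8.3.1 and 8.3.2 describe the same patients and differ only in as-randomised against as-treated analysis. That distinction means something only if patients given the other arm's treatment are included, and SAP 6.5.1.3 names study treatment as TheraSphere or sorafenib. Work-up failures who take sorafenib therefore probably stay in, which makes illustration (b) the less supported case. This stands, but 8.3.1 does not say so. Protocol 9.2.16.1.2 only permits sorafenib for such a patient, so one who takes neither treatment is still lost.

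A further reading would admit patients at first angiogram, where the SAP starts the TheraSphere arm's safety clock (6.2.1, 6.5.2). Section 6.5.1.3 weighs against it, but the ambiguity should be closed.

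Several secondary endpoints would barely move. Patients with no post-baseline assessment are censored at randomisation (or at death, for TTP) and add nothing to the FACT-Hep model. The material effect is on OS and the response rates. Protocol 10.2.5 names no population for baseline tables, so SAP 8.4 contradicts nothing there.

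The populations are stated openly in 8.3 and 8.9, and 8.1 reports randomised and treated counts. The SAP also discloses some other changes outside Section 5, but with a reason: small numbers for dropping site (7.2) and subgroups (7.7). No reason is given for dropping ITT, and early termination does not supply one, since a log-rank or Cox analysis on all randomised patients needs no minimum size.

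**Conclusion.** The concern holds. SAP 8.9 replaces the protocol's primary efficacy population without listing or justifying the change, and it conflicts with SAP 4.2. This should be corrected before the analysis is run.

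Size and direction of any bias cannot be determined, because the documents give neither untreated counts nor the prognosis of untreated patients. Under the milder assumptions, with each effect taken alone and losses in the TheraSphere arm, the apparent HR is about 0.95 to 0.99 when the truth is 1.00. With those failures lost from control instead it is 1.02 to 1.05. If work-up failures who take sorafenib stay in, the early-death effect in (a) is essentially all that remains. The harsher variant reaches 0.88. Start windows, failure rates and hazards are all assumed, and the permitted embolisation and dose reduction would lower the failure rate. Shifts of this size are mostly small beside sampling error, so the conclusion rests on the undeclared departure and not on any simulated HR.

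**What to change.** 1. Add an ITT population to SAP 8.3: every randomised patient, analysed in the arm assigned at randomisation.
2. Make it primary for OS and all secondary efficacy endpoints, including the response denominators in 8.9.2.4. Keep the Treated Population as a labelled sensitivity analysis. Present the baseline tables in 8.4 for ITT as well, so that they describe the patients analysed.
3. State in 8.3.1 whether sorafenib given to a TheraSphere-arm patient counts as study treatment, and whether an angiogram alone does.
4. Add to the counts in 8.1 the reasons for never starting treatment, by arm.
5. List in Section 5 any departure that remains, including the dropped per-protocol analysis, with the reason.

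The cost is SAP wording and an extra set of efficacy outputs, which spans three sets of tumour criteria and quality of life. No new patients or visits are needed, because both documents already keep untreated patients under follow-up. One limitation remains: untreated patients who withdraw early may be censored close to randomisation, because the contacts that SAP 6.4.1 uses (adverse event, lesion and best-available-care dates) may be sparse for them.
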